6.3. Randomization (Day 1)

The Randomization visit will occur within 14-28 days after the Screening visit on Day 1 (or within 14-60 days for subjects screening under Protocol Amendment 1). At the end of the Randomization visit, eligible subjects will be randomly assigned to receive GS-6615 or matching placebo.

The following will be performed and documented at the Randomization visit:

- Review inclusion and exclusion criteria to confirm continued eligibility
- Predose blood sample collection for plasma PK sample as described in Section 6.21 before the subject has taken the first dose of study drug
- **PPD**
- Urine pregnancy test for females of childbearing potential only
- Abbreviated physical examination including vital signs as described in Sections 6.18 and 6.19
- MLHFQ administration as described in Section 6.16
- Standard 12-lead resting ECG as described in Section 6.12
- For subjects with ICDs, perform ICD interrogation as described in Section 6.15
- Collect ZIO[®] XT Patch
- ZIO[®] XT Patch wear starts during the Randomization visit and continues for 14 days. Subjects will be provided with instructions for wear and removal of the patch. The ZIO[®] XT Patch will be collected at the Week 2 visit.
- Review of concomitant medications
- Review of adverse events
- After confirmation of eligibility, randomize subject via IXRS and dispense study drug. Provide subject with dosing instructions. Subject will take the Day 1 loading dose of study drug on site.
- Second blood sample collection for plasma PK sample as described in Section 6.21. The second PK sample should be collected 2-3 hours after the subject has taken the first dose of study drug. If 2-3 hours postdose collection is not possible, the second PK sample should be collected as late as possible before the subject leaves the clinic.
- Instruct the subject to hold the study drug dose on the day of the Week 2 visit so subject can take the study drug while on site.

6.4. Treatment Assessments: Double-Blind Treatment Period

6.4.1. Week 1 Contact

Subjects will be contacted on Day 7 \pm 3 days to review ongoing ZIO[®] XT Patch wear, adverse events and concomitant medications and to remind the subject to hold study drug dose on the day of the next visit so subject can take the study drug while on site.

6.4.2. Week 2 Visit

The Week 2 visit will occur on Day 14 (\pm 3 days). On the day of the visit, subjects should take study drug on site.

The following will be performed and documented at the Week 2 visit:

- Predose blood sample collection for plasma PK sample as described in Section 6.21. The first PK sample should be collected before the subject has taken the daily study drug dose at the site.
- Predose urine sample collection for urine PK as described in Section 6.21. The urine sample for PK should be collected before the subject has taken the daily study drug dose at the site.
- Blood and urine sample collection for Clinical Laboratory Assessments as described in Section 6.20
- Urine pregnancy test for females of childbearing potential only
- Witness daily study drug dosing after predose PK sample collection
- Abbreviated physical examination including vital signs as described in Sections 6.18 and 6.19
- Standard 12-lead resting ECG as described in Section 6.12
- ECHO as described in Section 6.14
- Collect ZIO[®] XT Patch
- Review of concomitant medications
- Review of adverse events
- Collect and review used and unused study drug for accountability and calculate compliance
- Dispense study drug

- Second blood sample collection for plasma PK sample as described in Section 6.21. The second PK sample should be collected approximately 3 hours after the subject has taken the daily dose of study drug. If 3 hours postdose is not possible, the PK sample should be collected as late as possible before the subject leaves the clinic.
- Instruct the subject to hold the study drug dose on the day of the next visit so the subject can take the study drug while on site.

6.4.3. Week 6 Visit

The Week 6 visit will occur on Day 42 (± 7 days). On the day of the visit, subjects should take study drug on site.

The following will be performed and documented at the Week 6 visit:

- Predose blood sample collection for plasma PK sample as described in Section 6.21. The first PK sample should be collected before the subject has taken the daily study drug dose at the site.
- Predose urine sample collection for urine PK as described in Section 6.21. The urine sample for PK should be collected before the subject has taken the daily study drug dose at the site.
- Blood and urine sample collection for Clinical Laboratory Assessments as described in Section 6.20
- Urine pregnancy test for females of childbearing potential only
- Witness daily study drug dosing after predose PK sample collection
- Abbreviated physical examination including vital signs as described in Sections 6.18 and 6.19
- Standard 12-lead resting ECG as described in Section 6.12
- ZIO[®] XT Patch wear starts at any time during the Week 6 visit and continues for 14 days. Subjects will be provided with instructions for wear and removal of the patch. The ZIO[®] XT Patch will be collected at the Week 12 visit.
- Review of concomitant medications
- Review of adverse events
- Collect and review used and unused study drug for accountability and calculate compliance
- Dispense study drug

- Second blood sample collection for plasma PK sample as described in Section 6.21. The second PK sample should be collected approximately 3 hours after the subject has taken the daily dose of study drug. If 3 hours postdose is not possible, the PK sample should be collected as late as possible before the subject leaves the clinic.
- Instruct the subject to hold the study drug dose on the day of the next visit so the subject can take the study drug while on site.

6.4.4. Week 9 Contact

Subjects will be contacted on Day 63 \pm 3 days to review ZIO[®] XT Patch wear/removal, adverse events and concomitant medications, remind the subject to hold study drug dose on the day of the next visit so subject can take the study drug while on site, and review the CPET restrictions for the next visit.

6.4.5. Week 12 Visit

The Week 12 visit will occur on Day 84 (\pm 7 days). On the day of the visit, subjects should take study drug on site. If needed, the Week 12 visit may be conducted over 2 consecutive days.

Recommended order of assessments at Week 12 visit: (1) predose PK sample collection, (2) witnessed study drug dosing, (3) MLHFQ, (4) ECG, (5) CPET, (6) ECHO, and (7) all other blood sample collection including postdose PK sample. All other required visit assessments may occur at any point during the study visit. It is important that the MLHFQ administration occurs prior to CPET.

The following will be performed and documented at the Week 12 visit:

- Abbreviated physical examination including vital signs as described in Sections 6.18 and 6.19
- Predose blood sample collection for plasma PK sample as described in Section 6.21. The first PK sample should be collected before the subject has taken the daily study drug dose at the site.
- Predose urine sample collection for urine PK as described in Section 6.21. The urine sample for PK should be collected before the subject has taken the daily study drug dose at the site.
- Witness daily study drug dosing after predose PK sample collection
- MLHFQ administration as described in Section 6.16
- Standard 12-lead resting ECG as described in Section 6.12
- For subjects with ICDs, perform ICD interrogation as described in Section 6.15
- Cardiopulmonary Exercise Testing (CPET) using the Modified Naughton Protocol as described in Section 6.11 and according to the study-specific CPET Manual

- ECHO as described in Section 6.14
- Blood and urine sample collection for Clinical Laboratory Assessments as described in Section 6.20
- Urine pregnancy test for females of childbearing potential only
- Blood sample collection for NT-proBNP and hsTnT testing
- Review of concomitant medications
- Review of adverse events
- Collect ZIO[®] XT Patch
- Collect and review used and unused study drug for accountability and calculate compliance
- Dispense study drug
- Second blood sample collection for plasma PK sample as described in Section 6.21. The second PK sample should be collected approximately 3 hours after the subject has taken the daily dose of study drug. If 3 hours postdose is not possible, the PK sample should be collected as late as possible before the subject leaves the clinic.
- Instruct the subject to hold the study drug dose on the day of the next visit so the subject can take the study drug while on site.

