3.7. Biomarker Testing

3.7.1. Biomarker Samples to Address the Study Objectives

Blood samples will be collected and used to evaluate the association of systemic biomarkers with study drug response, including efficacy and/or adverse events and to increase knowledge and understanding of the biology of HCM and related diseases. The specific analyses will include NT-proBNP and high-sensitivity Troponin T (hsTnT), but will not be limited to the biomarkers listed. Because biomarker science is a rapidly evolving area of investigation, and adverse events in particular are difficult to predict, it is not possible to specify prospectively all tests that will be done on the specimens provided. The testing outlined is based upon the current state of scientific knowledge and may change during or after the end of the study to remove tests no longer indicated and/or to add new tests based upon the growing state of art knowledge.

Blood samples will be collected from all subjects at Screening, Week 12, and Week 24 visits for analysis of NT-proBNP and high-sensitivity Troponin T (hsTnT). These are validated biomarkers of myocardial wall stress and microvascular ischemia respectively that have been shown to predict long-term prognosis in patients with HCM {Coats et al 2013}, {Kubo et al 2013}.

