6.2. Pretreatment Assessments

6.2.1. Screening Visit

Subjects will be screened within 14-28 days prior to the Randomization visit to determine eligibility for participation in the study. Subjects who are screen failures for any reason may only be re-screened with approval from the Medical Monitor. For subjects screening under Protocol Amendment 1 (10 October 2014), the Screening visit will be within 14-60 days prior to Randomization.

The following will be performed and documented at Screening:

- Obtain written informed consent prior to initiation of study procedures
- Review and record inclusion and exclusion criteria
- Obtain medical history including cardiovascular and surgical history, sarcomeric mutation if known, history of allergies, and history of prior (within previous 30 days) and current medication use. For female subjects, confirm documentation of childbearing potential as defined in [Appendix 8](#).
- Complete physical examination including vital signs, body weight, and height, as described in [Sections 6.18](#) and [6.19](#). Calculate BMI to confirm eligibility using body weight and height measurements.
- Standard 12-lead resting ECG as described in [Section 6.12](#)

- Cardiopulmonary Exercise Testing (CPET) using the Modified Naughton Protocol as described in Section 6.11 and according to the study-specific CPET Manual.
 - At the Screening visit, subjects are required to have a Screening (baseline) Peak VO₂ of < 80% of predicted based on age, sex, and weight-adjusted equations (Appendix 4).
Subjects whose baseline Peak VO₂ is ≥ 80% of predicted will not be eligible to continue.
- ECHO as described in Section 6.14, including measurement of left ventricular ejection fraction to confirm eligibility
- Collect blood and urine samples for Clinical Laboratory Assessments as described in Section 6.20
- Collect blood sample for serum pregnancy testing for females of childbearing potential only
- Blood sample collection for NT-proBNP and hsTnT testing
- ZIO[®] XT Patch wear starts at the end of the Screening visit and continues for 14 days. Subjects will be provided with instructions for wear and removal of the patch. The ZIO[®] XT Patch will be collected at the Randomization visit.
- Serious adverse events and all adverse events related to protocol-mandated procedures observed during the screening period are to be captured as adverse events

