6.4.9. Week 24 Visit

The Week 24 visit will occur on Day 168 (± 7 days). On the day of the visit, subjects should take study drug on site. If needed, the Week 24 visit may be conducted over 2 consecutive days.

In order to accumulate additional long-term safety in this population, subjects will continue double-blind treatment until the last subject has been followed up for approximately 24 weeks. As that date approaches, all remaining subjects (including subjects who have already discontinued treatment but who are continuing the study) will be contacted to return for the End of Double-Blind Treatment Period (EDBT) visit. For some subjects the Week 24 visit may also serve as the EDBT visit, see Section 6.4.11 for further detail.

Recommended order of assessments at Week 24 visit: (1) predose PK sample collection, (2) witnessed study drug dosing, (3) MLHFQ, (4) ECG, (5) CPET, (6) ECHO, and (7) all other blood sample collection including postdose PK sample. All other required visit assessments may occur at any point during the study visit. It is important that the MLHFQ administration occurs prior to CPET.

The following will be performed and documented at the Week 24 visit:

- Abbreviated physical examination including vital signs, as described in Sections 6.18 and 6.19
- Predose blood sample collection for plasma PK sample as described in Section 6.21. The first PK sample should be collected before the subject has taken the daily study drug dose at the site.
- Predose urine sample collection for urine PK as described in Section 6.21. The urine sample for PK should be collected before the subject has taken the daily study drug dose at the site.
- Witness daily study drug dosing after predose PK sample collection
- MLHFQ administration as described in Section 6.16
- Perception of Treatment Assignment Questionnaire administration as described in Section 6.17
- Standard 12-lead resting ECG as described in Section 6.12
- For subjects with ICDs, perform ICD interrogation as described in Section 6.15
- Cardiopulmonary Exercise Testing (CPET) using the Modified Naughton Protocol as described in Section 6.11 and according to the study-specific CPET Manual.
- ECHO as described in Section 6.14

- Blood and urine sample collection for Clinical Laboratory Assessments as described in Section 6.20
- Urine pregnancy test for females of childbearing potential only
- Blood sample collection for NT-proBNP and hsTnT testing
- Review of concomitant medications

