6.11.3.1. Conduct of CPET

The following instructions apply to the conduct of the exercise tests at the Screening, Week 12 and Week 24 visits, and if applicable, Early Termination visit. Please refer to the CPET study manual for full detail on required data collection during exercise testing.

- 1) Weigh the subject.
- 2) Provide detailed test instructions to the subject (Section 6.11.2).
- 3) Attach ECG electrodes to the subject in the standard 12-lead configuration and record baseline resting 12-lead ECGs in both the supine and standing positions.
- 4) Measure the subject's baseline resting blood pressure and heart rate in the supine and standing position.
- 5) Prior to beginning the Modified Naughton exercise protocol, allow the subject to stand on the treadmill or sit in a chair next to the treadmill and acclimate to the gas exchange equipment. Record the resting CPET data for a minimum of two minutes (and ideally until the subject's RER is between 0.70 and 0.85) prior to beginning the test. Make certain that the test starting point is clearly labelled in order to distinguish resting and exercise data.

- 6) Begin the Modified Naughton Protocol exercise test. Perform continuous, 3-lead minimum ECG monitoring, and print a 12-lead ECG each minute throughout the exercise test.
- 7) At the end of each minute, have the subject assign a Borg Scale ([Appendix 5](#)) rating between 6 and 20.
- 8) Record gas exchange data continuously. The CPET printout must show 30-second rolling averages collected every ten seconds for the entire test.
- 9) Measure the subject's blood pressure and heart rate within the last 30 seconds of each 2-minute exercise stage.
- 10) Maximal effort should be encouraged. The exercise test should be stopped based on standard indications for stopping (see Section [6.11.3.2](#)). At the time the exercise test is stopped (maximum exercise), a 12-lead ECG should be printed manually if the system does not print one automatically.

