6.22. NT-proBNP and High-sensitivity Troponin T (hsTnT) Samples

Blood samples for analysis of NT-proBNP and hsTnT prognostic biomarkers will be collected at Screening, Week 12, and Week 24 visits. Refer to Section 3.7.1 for further detail on biomarker sample collection.

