Appendix 2. Study Procedures Table

	Screening Period		Double-Blind Treatment Period						OLE	Follow-up
	Screening Visit	Randomization Visit	Week 2 Visit	Week 6 Visit	Week 12 Visit ^a	Week 18 Visit	Week 24 Visit ^a	Every 12 weeks after Week 24 through EDBT visit	Visits at OLE Weeks 12, 24, & then every 24 weeks	30-day Follow-up Visit -or- ET Visit ^b
	Day -28 to Day -14	Day 1	Day 14 ±3 days	Day 42 ±7 days	Day 84 ±7 days	Day 126 ±7 days	Day 168 ±7 days			
Written Informed Consent	X									ET only ^b
Inclusion/Exclusion Criteria Review	X	X								
Medical History	X									
Physical Exam ^c	X	X	X	X	X	X	X	X	X	X
Vital Signs	X	X	X	X	X	X	X	X	X	X
Study drug dosing during visit ^d		X	X	X	X	X	X	X	OLE Wk 12 & OLE Wk 24 only	
MLHFQ ^e		X			X		X			ET only ^g
Perception of Treatment Assignment Questionnaire ^f							X			ET only ^g
12-Lead resting ECG	X	X	X	X	X	X	X	X	X	X
CPET/Peak VO ₂ measurement	X				X		X			ET only ^g
Echocardiogram	X		X		X		X			ET only
ICD interrogation		X			X		X			ET only ^g
Clinical Laboratory Assessments ^h	X		X	X	X	X	X	X	X	X
Pregnancy Test ⁱ	X	X	X	X	X	X	X	X	X	X
PK sample collection		X ^j	X ^k	X ^k	X ^k	X ^k	X ^k	X ^k	X ^{kl}	X ^l

	Screening Period		Double-Blind Treatment Period						OLE	Follow-up
	Screening Visit	Randomization Visit	Week 2 Visit	Week 6 Visit	Week 12 Visit ^a	Week 18 Visit	Week 24 Visit ^a	Every 12 weeks after Week 24 through EDBT visit	Visits at OLE Weeks 12, 24, & then every 24 weeks	30-day Follow-up Visit -or- ET Visit ^b
	Day -28 to Day -14	Day 1	Day 14 ±3 days	Day 42 ±7 days	Day 84 ±7 days	Day 126 ±7 days	Day 168 ±7 days			
NT-proBNP & hsTnT	X				X		X			
Optional PG sample collection ^m		X								
Start ZIO [®] XT Patch (14 day wear)	X	X		X		X				
Collect ZIO [®] XT Patch		X	X		X		X			
Dispense Study Drug		X	X	X	X	X	X	X	X	
Study Drug Accountability & Compliance			X	X	X	X	X	X	X	X ⁿ
Contact Subject ^o									X ^p	
Concomitant Medications	X	X	X	X	X	X	X	X	X	X
Adverse Events	X	X	X	X	X	X	X	X	X	X

- a Recommended order of assessments at Week 12 and Week 24 visits: (1) predose PK sample collection, (2) witnessed study drug dosing, (3) MLHFQ, (4) ECG, (5) CPET, (6) ECHO, and (7) all other blood sample collection including postdose PK sample. All other required visit assessments may occur at any point during the study visit. For Week 24 visit only: For some subjects, Week 24 visit is the same as the End of Double-Blind Treatment Period Visit

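### NT-proBNP and hsTnT are recommended to be drawn after a maximal CPET at Weeks 12 and 24 but in no set order at Screening, so within-arm change from baseline may include an exercise component

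*Protocol*

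**What the plan says.** **Weeks 12 and 24.** Protocol 6.4.5 and 6.4.9 give the same sequence. At Week 24 it begins "Recommended order of assessments at Week 24 visit: (1) predose PK sample collection, (2) witnessed study drug dosing, (3) MLHFQ, (4) ECG, (5) CPET, (6)"; at both visits it ends "5) CPET, (6) ECHO, and (7) all other blood sample collection including postdose PK sample". Only the predose PK sample is drawn earlier. Appendix 2, footnote a, repeats this under the words "Recommended order of assessments at Week 12 and Week 24 visits". For the exercise test itself, Protocol 6.11.3.1 says "Maximal effort should be encouraged". Section 6.4.5 adds "If needed, the Week 12 visit may be conducted over 2 consecutive days", and 6.4.9 allows the same at Week 24.

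**Screening.** Protocol 6.22 states "Blood samples for analysis of NT-proBNP and hsTnT prognostic biomarkers will be collected at Screening, Week 12, and Week 24 visits". Section 6.2.1 lists the CPET and, further down, "Blood sample collection for NT-proBNP and hsTnT testing". It does not say which comes first, and footnote a does not cover Screening.

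**Baseline in the SAP.** The schedule text in SAP 1.2 places the NT-proBNP and hsTnT samples at Day 1. The procedures table in SAP Appendix 1 places them at Screening, as the protocol does. SAP 3.7 takes the last record on or before the first dose date as baseline.

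**Use of the data.** Protocol 8.8 compares log-transformed changes with placebo by ANCOVA, adjusted for sex, age and baseline, and also summarises change by arm. SAP 6.6 drops inferential statistics for exploratory endpoints. SAP 3.8.2 still has biomarker results summarised by visit.

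**The concern.** Protocol 3.7.1 calls the two markers "validated biomarkers of myocardial wall stress and microvascular ischemia respectively". A maximal treadmill test in symptomatic HCM may provoke both processes; the CPET stopping rules in 6.11.3.2 provide for angina and marked ST displacement. A sample taken after such a test may therefore not measure the same thing as a resting sample.

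The follow-up samples are recommended to be post-exercise, while the baseline sample may be resting, post-exercise or a mixture across sites. The delay after exercise is also loose. Step 7 groups these draws with the postdose PK sample, due about 3 hours after dosing or as late as possible, and the visit may run into a second day. The protocol does guard the MLHFQ against order effects by requiring it before the CPET, but it gives the biomarkers no such protection.

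At stake is how the by-arm changes are read. With no inferential comparison in the final SAP, those descriptive changes are what a reader will see.

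**Working it through.** The plan states no figure on this point, so there is none to reproduce. The size of any acute exercise effect, the mix of Screening draw orders and any difference between arms are all assumptions.

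**1. Within-arm change.** Let *g* be the factor by which a post-CPET value exceeds a resting value, *q* the share of baseline samples drawn after CPET, and *d* the drug's effect on the resting value as a ratio. With every follow-up sample drawn after CPET, the expected log change in an arm is

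log *d* + (1 − *q*) log *g*.

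With no drug effect (*d* = 1), the ratio to baseline is *g*^(1−*q*):

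| Assumed acute rise | All baselines resting (*q* = 0) | Half and half (*q* = 0.5) | All baselines post-CPET (*q* = 1) |
|---|---|---|---|
| 10% | 1.10 | √1.10 = 1.049 | 1.00 |
| 25% | 1.25 | √1.25 = 1.118 | 1.00 |
| 50% | 1.50 | √1.50 = 1.225 | 1.00 |

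A Day 1 baseline, as in SAP 1.2, would correspond to *q* = 0, because no CPET is scheduled at Randomization.

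**2. Comparison with placebo, equal acute response.** The term (1 − *q*) log *g* is the same in both randomised arms, so active minus placebo is log *d*. A simulated ANCOVA agrees. It used 180 subjects, 2000 runs per setting, an assumed log SD of 1.0 and correlation of 0.85, *g* from 1.00 to 1.30, and *q* of 0, 0.5 and 1:

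- The mean treatment difference lay between −0.004 and 0.002 on the log scale.
- Rejection at a nominal 5% ranged from 3.7% to 5.6%. The Monte Carlo standard error is √(0.05 × 0.95 / 2000) = 0.5 percentage points. At *q* = 0 or 1 a common effect only adds a constant and cannot change the test.
- The standard error rose from 0.0785 to at most 0.0803 (0.0803 / 0.0785 = 1.02), at *g* = 1.30 and *q* = 0.5.

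A common effect therefore costs a little precision and causes no bias.

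**3. Comparison with placebo, different acute response.** Let the acute rise be *r* on placebo and *r*(1 + *w*) on active, with no drug effect at rest. The spurious between-arm ratio is (1 + *r*(1 + *w*)) / (1 + *r*):

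- *r* = 0.10, *w* = 0.10: 1.11 / 1.10 = 1.009
- *r* = 0.10, *w* = 0.20: 1.12 / 1.10 = 1.018
- *r* = 0.50, *w* = 0.10: 1.55 / 1.50 = 1.033
- *r* = 0.50, *w* = 0.20: 1.60 / 1.50 = 1.067

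If the drug blunts the response instead:

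- *r* = 0.10, *w* = −0.10: 1.09 / 1.10 = 0.991
- *r* = 0.50, *w* = −0.20: 1.40 / 1.50 = 0.933

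A second parametrisation, with the active arm's log response *k* times placebo's, gives *g*^(*k*−1). At *g* = 1.30 this is 0.937 for *k* = 0.75 and 1.068 for *k* = 1.25, which is of similar size.

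**The case against.** The strongest reply is that the drug effect is judged against placebo. Both arms follow one schedule, and the Screening order is settled before randomisation. A common exercise effect therefore cancels, as step 2 of the working shows. This stands. A reader might infer that the drug effect itself is confounded with exercise; the documents do not support that.

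A reader might also infer bias against the drug, since longer treadmill time is a hoped-for effect (Protocol 8.1.3) and would mean sampling after more work. That is not supported either. Protocol 1.3 expects late sodium current inhibition to act on diastolic dysfunction and microvascular ischemia, which could blunt the marker response. Either sign is possible, and no bias arises unless the acute response differs by arm.

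Three further objections have weight:

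- No passage says that either marker moves measurably between a treadmill test and a same-visit draw. The existence of the effect is assumed, as well as its size.
- The order is recommended and visits may be split over two days, so some follow-up samples may have preceded the CPET.
- The Screening list itself runs CPET, ECHO, laboratory blood, then biomarkers. If sites followed it, and the exercise effect was the same at each visit, the within-arm shift disappears. Study manuals not available here may also say more.

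What survives is that the plan recommends one order after baseline, fixes none at baseline, and gives two accounts of when the baseline sample is taken.

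**Conclusion.** The point holds for within-arm change from baseline. If exercise acutely raises these markers by 10% to 50%, a resting baseline and no drug effect would give a ratio of 1.10 to 1.50 in both arms; the shift is smaller with mixed baselines and zero if all baselines were also post-CPET. The comparison with placebo is unbiased unless the acute response differs by arm. In that case the error is roughly 1% to 7%, in either direction, for 10% to 20% more or less acute response. All these ranges are assumptions.

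The consequence is small. The markers are exploratory, the final SAP makes no inferential comparison of them, and the primary and secondary endpoints are untouched. This is a free improvement.

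**What to change.** **Protocol.** In 6.4.5, 6.4.9 and Appendix 2 footnote a, place the NT-proBNP and hsTnT draw with the predose PK sample at step 1. In 6.2.1, state that the Screening sample is drawn before the CPET. Record draw and CPET times at all three visits. Clinical laboratory blood can stay where it is; no problem is shown for it. Drawing all samples after CPET would remove the within-arm shift only if the acute response is equal across visits; drawing all before also removes any between-arm term.

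**SAP.** Reconcile the Day 1 sampling in SAP 1.2 with the Screening sampling in SAP Appendix 1 and Protocol 6.22, so that the baseline sample is unambiguous.

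**Data already collected.** SAP 2 records that the study was terminated, so the protocol edits matter for any reuse of the design. In the report, use recorded times where available to show which samples preceded or followed CPET. State that a post-CPET draw was recommended at Weeks 12 and 24 and that the Screening order was unspecified. Do not label every value post-exercise, since some may not be.

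**Cost.** One sentence in each of four protocol places, two recorded times and one SAP correction. A venepuncture already takes place at step 1, so no visit or needle stick is added.
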